#### 9.4.3 Patient Global Impression of Change (PGI-C)

The patient global impression of change (PGI-C) includes 1 question of “How would you compare the impact of your anemia and its treatment on how you feel now to when you were on the previous treatment (or the period your last visit)?” There are 7 patient responses for selection: very much worsened, much worsened, minimally worsened, no changed, minimally improved, much improved, and very much improved.

---

The PGI-C will be summarized with the number and percentage of subjects with response by treatment.

#### **9.4.4 HRQOL measure EuroQol 5 Dimensions 5 Levels (EQ-5D-5L)**

EQ-5D-5L includes 5 questions with “Under each heading, please check the ONE that best describes your health TODAY”:

1. Mobility with 5 responses:
  - a. I have no problems walking
  - b. I have slight problems walking
  - c. I have moderate problems walking
  - d. I have severe problems walking
  - e. I am unable to walk
  
2. Self-care with 5 responses:
  - a. I have no problems washing or dressing myself
  - b. I have slight problems washing or dressing myself
  - c. I have moderate problems washing or dressing myself
  - d. I have severe problems washing or dressing myself
  - e. I am unable to wash or dress myself
  
3. Usual activities with 5 responses:
  - a. I have no problems doing my usual activities
  - b. I have slight problems doing my usual activities
  - c. I have moderate problems doing my usual activities
  - d. I have severe problems doing my usual activities
  - e. I am unable to do my usual activities
  
4. Pain/Discomfort with 5 responses:
  - a. I have no pain or discomfort
  - b. I have slight pain or discomfort
  - c. I have moderate pain or discomfort
  - d. I have severe pain or discomfort
  - e. I have extreme pain or discomfort
  
5. Anxiety / Depression with 5 responses:
  - a. I am not anxious or depressed
  - b. I am slightly anxious or depressed
  - c. I am moderately anxious or depressed
  - d. I am severely anxious or depressed

---

- e. I am extremely anxious or depressed

EQ-5D-5L data will be summarized with the number and percentage of subjects with response by treatment.

In addition, the last question of EQ-5D-5L include “We would like to know how good or bad your health is TODAY.” A 0-100 scale will be marked by each patient using “X” and as a score of 0-100 will be recorded by the patient 0 indicates the worst health you can imagine and 100 indicates the best health you can imagine. This health score of today will be summarized by treatment group with descriptive statistics including the number of subjects, mean, median, standard deviation and range.

## **9.5 Additional Sensitivity Analyses**

Due to the Eurofins Ransomware Attack, the analysis of primary endpoint with excluding subjects who were randomized before July 23, 2019 for vadadustat group will be provided as sensitivity analyses.

For the above-mentioned efficacy endpoints, additional sensitivity analyses may be performed.

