## 2 STUDY OBJECTIVE AND DESIGN

### 2.1 Study Objectives

#### 2.1.1 Primary Objective

To assess the efficacy and safety of daily dosing of vadadustat compared to epoetin alfa for 12 weeks in hemodialysis subjects.

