### **3.4 Epoetin Alfa Treatment**

Subjects in both the Main study and ESA hyporesponder parallel study randomized to epoetin alfa:

All subjects randomized to epoetin alfa will receive TIW dosing for the entire Treatment Period based on the subject's central laboratory Hb value and the approved epoetin alfa US Package Insert (PI) for adult patients with CKD on dialysis. Dose will be adjusted to achieve and maintain Hb levels within the target range of 10.0 to 11.0 g/dL, inclusive, while targeting the middle of the range and minimizing excursions outside of the target range.

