#### 4 CHANGES FROM THE PROTOCOL

No changes in planned analyses were done compared to the protocol in this SAP. But due to the Eurofins Ransomware Attack, the change from baseline in Hemoglobin (Hb, g/dL) with excluding subjects who were randomized before July 23, 2019 for vadadustat group will be provided as sensitivity analyses.

---

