## 8 STUDY ANALYSES

### 8.1 General Consideration

The following rules will be adopted when summarizing the data:

1. The Main Study and the ESA Hyporesponder Parallel Study will be summarized separately, but in an analogous manner, for all endpoints.
  - a. For the Main study, the low epoetin dose group ( $\leq 90$  U/kg/week), 450 mg of vadadustat, 300 mg of vadadustat and epoetin will be displayed side by side. In addition, the total vadadustat will be presented as well.
  - b. For the Main study, the high epoetin dose group ( $> 90$  and  $< 300$  U/kg/week), 600 mg, 450 mg, 300 mg of vadadustat and epoetin will be displayed side by side. In addition, the total vadadustat will be presented as well.
  - c. For the Main study, a summary of total vadadustat vs. epoetin will be presented as well. For the background information, a total column for all randomized patients will be presented except certain PK/PD parameters.
  - d. For the ESA Hyporesponder Parallel Study ( $\geq 300$  U/kg/week), 600 mg and epoetin will be displayed side by side.
2. For efficacy data analysis, 3 tables will be presented for some selected efficacy endpoints:
  - a. Overall summary by week including the first weeks and post Week 12 by treatment group which is based on the randomized dose group.
  - b. For subjects who switched Vadadustat dosing from QD to TIW dosing.
  - c. For subjects who did not switch from QD to TIW dosing after Week 12.
3. For safety data analysis, 5 sets of tables will be presented for some selected safety parameters:
  - a. Overall summary for all weeks including the first 12 weeks and post Week 12 by treatment group
  - b. Overall summary for the first 12 weeks of treatment.
  - c. Overall summary for Weeks 12 to the end of study for both switched and not switched patients at Week 12
  - d. Overall summary for Weeks 12 to the end of study for switched patients
  - e. Overall summary for Weeks 12 to the end of study for not switched patients
4. For patients who switched Vadadustat dosing from QD to TIW dosing at week 12, and then switched back to QD, if there are less than or equal to 20 subjects, only patient

---

listings/profiles will be created. If there are more than 20 patients, summary tables will be created by treatment groups for efficacy and safety.

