### 9.3 Other Secondary Endpoints

- Intravenous (IV) iron supplementation and oral iron

The average weekly elemental iron use during the treatment period which is defined as first dose date to last dose date + 7 days will be calculated for weekly intervals from both oral and IV iron medications (Oral iron dose will be converted to elemental iron dose; the list will come from the medical team.). The treatment period will be divided in periods of 7 days and for each of these periods the weekly mean of IV iron will be used using the following formula:

$$\text{Weekly iron use for each subject} = \text{Total iron in mg} / [(\text{last dose date} + 7 - \text{first dose date} + 1) / 7]$$

The average weekly iron use will be summarized by treatment group using descriptive statistics. The content of elemental iron for different kinds of IV iron is presented in [Appendix 5](#).

In addition, numbers and percentages of subjects with at least one administration of elemental iron will be summarized by treatment group.

- ESA administration and RBC transfusion

ESA medication will be considered as rescue if the ESA medication was taken between the first dose date to the last dose date + 7 days and the reasons for the ESA medication use is checked as confirmed Hb  $< 8.5$  g/dL on the CRF and the ESA medication wasn't taken during the period of Eurofins ransomware attack (after Jun 20, 2019 and before July 9, 2019).

---

Epoetin alfa dose will be administered based on the subject's central laboratory Hb value and the approved epoetin alfa US PI for adult patients with CKD on dialysis. From Baseline/Day 1 to Week 20, dose will be adjusted to achieve and maintain Hb levels within the target range of 10.0 and 11.0 g/dL, inclusive. Because epoetin alfa is titratable, increase in dose is not considered rescue unless the investigator specifically designates it as such; however, increases in dose relative to last dose will be characterized in three categories by percentage increase: <50%, ≥50% and <100%, and ≥100%. In addition to the investigator's judgement of rescue, the increase in dose ≥50% or ≥100% will be considered as additional conditions for ESA rescue in EPO group.

RBC transfusion will be considered as rescue if the RBC transfusion was taken between the first dose date to the last dose date + 7 days and the reasons for the RBC transfusion is checked as Worsening Anemia due to CKD on the CRF.

[figure not shown]

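### The ransomware sensitivity analysis excludes early-randomized subjects from the vadadustat group only, with no stated reason, so it has no matching epoetin comparator

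*SAP*

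**What the plan says.** SAP Section 9.5 specifies the sensitivity analysis of the primary endpoint for the attack with the words "excluding subjects who were randomized before July 23, 2019 for vadadustat group will be provided as sensitivity analyses". Section 4 repeats the restriction for change from baseline in Hb: "excluding subjects who were randomized before July 23, 2019 for vadadustat group". No section applies the exclusion to epoetin alfa, and none explains why the arms are treated differently.

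Four other places bear on the rule:

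- Section 9.3 dates the attack, for the purpose of classifying ESA rescue, as "after Jun 20, 2019 and before July 9, 2019".
- Section 3.4 bases epoetin dosing on the "central laboratory Hb value and the approved epoetin alfa US Package Insert". Section 9.3 says the same again.
- Section 2.1.1 gives the primary objective as a comparison: "To assess the efficacy and safety of daily dosing of vadadustat compared to epoetin alfa for 12 weeks in hemodialysis subjects".
- Section 8.1 has the dose groups and epoetin displayed side by side and adds, for the Main study, that "a summary of total vadadustat vs. epoetin will be presented as well".

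**The concern.** Randomization date is known at baseline. Cutting both arms at the same date leaves a smaller randomized comparison, restricted to later enrollees. Cutting one arm does not: what remains in that arm enrolled later than the arm it is set against. Any feature of the trial that changed over calendar time, such as site mix or experience with titration, would then be removed from vadadustat and left in epoetin, along with any effect of the attack on epoetin dosing.

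What is at stake is the purpose of the table. A reader would use it to ask whether the primary result survives the laboratory disruption. If it differs from the primary analysis, the reader cannot tell an attack effect from a calendar difference between the arms. If it agrees, the two may have offset each other.

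The cut-off date raises a second, smaller question. The SAP does not say how a randomization date of 23 July 2019 follows from the attack dates it gives elsewhere.

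**Working it through.** The SAP states no figure for this analysis, so there is nothing of its own to reproduce. The check consists of date arithmetic and a short derivation.

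**Inputs.** Attack period: after 20 June and before 9 July 2019 (Section 9.3). Cut-off: randomized before 23 July 2019 (Sections 4 and 9.5). The Week 12 analysis window ends on Day 88 (Section 6, visit table). Baseline is the mean of the last two Hb values before dosing (Section 9.1). Screening lasts at most 28 days (Section 3.1). I take randomization and Day 1 as the same date and assume the baseline Hb values fall within screening.

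**Dates.**

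- Attack window: 21 June to 8 July inclusive = 10 + 8 = 18 days.
- Gap from 9 July to the 23 July cut-off: 14 days.
- Day 88 = Day 1 + 87 days. For Day 88 to fall on or before 20 June 2019, Day 1 must be on or before 20 June − 87 days = 25 March 2019. Any vadadustat subject that early would have completed the primary window before the attack and would still be excluded.
- 8 July + 28 days = 5 August 2019. A subject randomized between 23 July and 5 August could have a baseline Hb drawn during the attack and would be kept.

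So the cut can remove unaffected subjects and keep affected ones. Whether such subjects exist cannot be seen from the SAP.

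**Effect on the arm contrast, if both arms are shown.** Let the mean Hb change be μE for early and μL for late enrollees under epoetin, with d = μL − μE. Let τ be a constant treatment difference, and f the share randomized before the cut, equal in expectation between arms by randomization.

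- Vadadustat, late only: μL + τ
- Epoetin, all dates: f·μE + (1 − f)·μL
- Difference: τ + f·(μL − μE) = τ + f·d
- Same cut in both arms: (μL + τ) − μL = τ, so the shift is 0

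The SAP gives neither f nor d. Illustrative values of f × d in g/dL:

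| f | d = 0.1 | d = 0.2 | d = 0.3 | d = 0.5 |
|---|---|---|---|---|
| 0.25 | 0.025 | 0.05 | 0.075 | 0.125 |
| 0.50 | 0.05 | 0.10 | 0.15 | 0.25 |
| 0.75 | 0.075 | 0.15 | 0.225 | 0.375 |

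A simulation with no treatment effect, d = 0.3 and SD 1 g/dL agrees. The one-arm cut gave 0.078, 0.145 and 0.232 for f = 0.25, 0.50 and 0.75. The two-arm cut gave 0.003, −0.009 and 0.013, which is zero within simulation error.

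**If only vadadustat is shown.** The formula does not apply. The table then gives a within-arm change with no epoetin subjects from the same enrolment period beside it, and does not address the comparison in the primary objective.

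**The case against.** The strongest reply is that little depends on this table. Section 9 plans no inferential modelling, Section 7 describes the study as exploratory and not sized on power, and the primary endpoint is still summarized for the Randomized, FAS and PP populations without this exclusion. That stands. A reader might infer that the trial's randomized comparison is lost; the SAP does not support this, because only the supplementary analysis uses the exclusion.

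Second, the primary endpoint is a mean change within each group, and the wording may mean a vadadustat-only table. That reading is open. Section 8.1 favours side-by-side display but does not settle it. The ambiguity changes the form of the problem without removing it.

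Third, a reader might infer that the attack is known to have affected both arms. The SAP does not say what happened to Hb reporting or dosing in either arm. It shows only that epoetin dosing also relies on the central laboratory, so that arm could be affected, and that no reason is given to treat it as spared.

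Fourth, a reader might conclude that 23 July has nothing to do with exposure. That goes too far. With up to 28 days of screening, a cut somewhat after 8 July could be meant to protect baseline Hb. The date is unexplained, which is a lesser fault.

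Finally, the SAP gives no enrolment dates, so the group with Day 1 by 25 March 2019 may be empty, and no figure for bias can be read from the document.

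**Conclusion.** The point holds for this one descriptive sensitivity analysis. As written, the exclusion applies to vadadustat alone without justification. Shown beside epoetin, it gives a non-concurrent comparison; shown alone, it has no concurrent comparator. In neither case can it tell the reader whether the vadadustat–epoetin comparison is robust to the attack.

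The size cannot be determined from the SAP. The shift is f × d, which is 0.025 to 0.375 g/dL over the assumed ranges f = 0.25 to 0.75 and d = 0.1 to 0.5 g/dL. This rests on the early/late difference being the same in both arms and on both arms being displayed. With no early/late difference the shift is zero. The harm is to interpretation: no test is planned, so no error rate is affected, and the primary analysis is unchanged.

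**What to change.** Amend Sections 4 and 9.5 so that one rule applies to vadadustat and epoetin alike, within dose stratum in the Main study and likewise in the ESA hyporesponder study. Either of these would do:

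- Keep a randomization-date cut and apply the same date to both arms.
- In both arms, exclude subjects whose interval from the first of the two baseline Hb values to Day 88 overlaps 21 June to 8 July 2019. Take Day 88 as the calendar date Day 1 + 87, whether or not the subject was still being followed, so that dropout does not decide who is excluded.

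State that both arms are shown, and add a sentence on how the chosen date or interval relates to the attack period in Section 9.3.

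The cost is a few sentences in the SAP and one changed filter in the programs, with no new data. The drawback is fewer epoetin subjects in this one table.

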## 10 SAFETY ANALYSIS

The safety analysis will be performed using the Safety Population. Safety parameters include adverse events, laboratory parameters, vital signs, ECG parameters, and physical examinations. For selected safety data, in addition, to the regular safety summary, for Weeks 12 – 20, patients who switched from daily vadadustat dose to TIW and patients who did not switch at Week 12 will be summarized separately.

### 10.1 Adverse Events

Safety analyses will be descriptive in nature.

All AEs will be coded using MedDRA version 23.0.

An AE (classified by preferred term) started during the treatment period will be considered a treatment-emergent adverse event (TEAE) if it was not present prior to the first dose of study medication, or it was present prior to the first dose of study medication but increased in severity during the treatment period. An AE that occurs more than 28 days after the last dose of study medication will not be counted as a TEAE.

The number and percentage of subjects reporting TEAEs in each treatment group and each treatment period will be tabulated by system organ class and preferred term; by system organ class, preferred term, and severity; and by system organ class, preferred term, and relationship to study medication. If more than one event occurs with the same preferred term for the same patient, the patient will be counted only once for that preferred term using the most severe and most related occurrence for the summarization by severity and by relationship to the study medication.

The distribution of TEAEs by severity and relationship to study medication will be summarized by SOC and PT and treatment group. AEs will also be summarized by their maximum severity.

Summaries will also be provided for the following types of TEAEs:

- SAEs
- Related TEAEs, as determined by the Investigator
- TEAEs leading to early discontinuation of study drug
- Adverse events of special interest (AESI); AESI is defined in [Appendix 4](#).

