### **3.2 Study Treatment Period (Baseline/Day 1 to Week 20)**

For all subjects (Main study and ESA hyporesponder parallel study), the Treatment Period will run from Baseline/Day 1 to Week 20. Dose will be adjusted to achieve and maintain Hb levels within the target range of 10.0 to 11.0 g/dL, inclusive, while targeting the middle of the range and minimizing excursions outside of the target range.

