### **3.5 Safety Follow-Up Period (Weeks 20 to 24)**

For all subjects (Main study and ESA hyporesponder parallel study), the 4-week Safety Follow-Up Period starting at Week 20 will be followed by a post-treatment safety assessment conducted at the beginning of Week 24.

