| Week 12 / Day 85                   | Day 82-88                     | Visit 9 / Week 12              |
| Week 13 / Day 92                   | Day 89-95                     | Visit 10 / Week 13             |
| Week 14 / Day 99                   | Day 96-105                    | Visit 11 / Week 14             |
| Week 16 / Day 113                  | Day 106-119                   | Visit 12 / Week 16             |
| Week 18 / Day 127                  | Day 120-133                   | Visit 13 / Week 18             |
| Week 20 / Day 141                  | Day 134 - (last dose day + 7) | Visit 14 / Week 20             |
| Follow up / Day last dose day + 28 | ≥ last dose day + 8           | Visit 15 / Week 24 (Follow up) |

Note: Week 20 is the end of treatment.

It is expected that some subjects will discontinue Follow-Up. The reasons for any missing data will be summarized by treatment arm. The primary analysis will be based upon observed data without imputation. As a sensitivity analysis for primary efficacy endpoint, missing Hb in weeks 10 to 12 will be imputed using last observation carried forward (LOCF). Similarly, for certain secondary efficacy endpoints, missing Hb in weeks 18-20 will be imputed using LOCF.

---

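### The TEAE onset clause ends at Week 20 but the cut-off is 28 days after last dose, so completers' follow-up AEs and worsening of continuing pre-dose AEs fall outside the TEAE tables

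*SAP*

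**What the plan says.** Section 10.1 opens its definition with an onset condition: "An AE (classified by preferred term) started during the treatment period will be considered a treatment-emergent adverse event (TEAE". The same sentence then gives two alternatives. Either the event was absent before the first dose, or "it was present prior to the first dose of study medication but increased in severity during the treatment period". The next sentence gives the only outer limit: "An AE that occurs more than 28 days after the last dose of study medication will not be counted as a TEAE".

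Section 10.1 does not define the treatment period. The design section does: "the Treatment Period will run from Baseline/Day 1 to Week 20". Section 3.5 treats what comes after as something else: "the 4-week Safety Follow-Up Period starting at Week 20 will be followed by a post-treatment safety assessment". The visit-window table in Section 6 puts the end of treatment at "Week 20 / Day 141".

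Section 10.1 then lists SAEs, investigator-related events, events leading to discontinuation of study drug and AESI as types of TEAE, so the definition decides what enters those tables.

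**The concern.** The onset clause and the 28-day sentence give different answers for an event that starts in the Safety Follow-Up Period of a subject who finished treatment. Under the onset clause it is not treatment-emergent. The 28-day sentence, by its choice of limit, implies that it should be. Two programmers could follow the text in good faith and produce different tables.

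If the clauses are applied together, the result is consistent but uneven. The number of post-dose days that count shrinks as the last dose moves later, and reaches zero for a completer. If discontinuation differs between arms, the arms are followed for TEAEs over windows of different length after the last dose, in an open-label trial whose safety comparison is descriptive. The SAP gives no expected discontinuation rates, so the size of any imbalance cannot be worked out.

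The onset clause also governs the worsening alternative in its own sentence. An event already present before the first dose, if held as one record, did not start on treatment, so it fails before its worsening is considered.

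**Working it through.** **Inputs**
- Treatment Period: Day 1 to Week 20 (Section 3.2).
- Week 20 target day: Day 141, noted as the end of treatment (Section 6, Table 1).
- Outer limit: last dose + 28 days (Section 10.1).
- Assumption: a completer's last dose falls on Day 141.

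The SAP states no figure of its own on this point, so there is none to reproduce.

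**Window length.** Let L be the day of last dose. The 28-day limit falls on day L + 28. The onset clause closes on Day 141. With both applied, the last countable onset day is the smaller of the two, so

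days lost = max(0, (L + 28) − 141) = max(0, L − 113).

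| Last dose (L) | 28-day limit | Last countable day, both clauses | Days lost | Share of window |
|---|---|---|---|---|
| Day 141 | Day 169 | Day 141 | 28 | 28/169 = 16.6% |
| Day 127 | Day 155 | Day 141 | 14 | 14/155 = 9.0% |
| Day 113 | Day 141 | Day 141 | 0 | 0% |
| Day 85 | Day 113 | Day 113 | 0 | 0% |

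Before Day 113 the 28-day sentence is the binding limit. After it, the onset clause is.

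**Individual records.** Each case is tested against the literal text (onset from Day 1 to Day 141; term absent before dosing, or present and worse; not beyond last dose + 28), and then against a window from first dose to last dose + 28 days that counts onset or worsening. Last dose is Day 141 throughout.

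| Record | Literal text | 28-day window with worsening |
|---|---|---|
| New AE, onset Day 50 | TEAE | TEAE |
| New AE, onset Day 155 | not a TEAE | TEAE |
| New AE, onset Day 175 | not a TEAE | not a TEAE |
| Onset Day −10, one continuing record, worsens Day 50 | not a TEAE | TEAE |
| Same preferred term before dosing, worsening entered as a new record on Day 50 | TEAE | TEAE |

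The definitions disagree on two of the five: the follow-up onset and the continuing record that worsens.

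**The case against.** The best defence is that the intention can be recovered. Section 8.1 plans safety tables from Week 12 to the end of the study, Section 8.8 counts concomitant medication to last dose + 4 weeks, and Section 10.1 names 28 days. Together these point to a window from first dose to last dose + 28 days. The 28-day sentence is also not idle under a fixed Week 20 limit, since it binds for anyone stopping before Day 113. Both points are correct, but neither removes the onset clause, which the programmer still has to apply or ignore. The study is exploratory and its safety analysis descriptive, which limits the consequences.

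Several stronger readings are tempting and are not supported:

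- *The worsening alternative can never be met.* Events are classified by preferred term, so a worsening entered as a new on-treatment record of a term present before dosing meets every condition. How worsening is recorded depends on CRF conventions not shown, so total exclusion of worsened events cannot be claimed.
- *Early stoppers lose most, for example half the window after stopping on Day 28.* Under Section 3.2, the 28-day limit for that subject is Day 56, inside the Treatment Period, and nothing is lost. The half (28/56) needs a period that ends at each subject's last dose, which the SAP does not state.
- *The loss is 21 of 169 days (12.4%).* This borrows "the treatment period which is defined as first dose date to last dose date + 7 days" from Section 9.3, where it is written for iron use and not for adverse events.
- *The discontinuation table loses follow-up onsets.* An event that starts after the last dose cannot have caused study drug to be stopped.
- *Every AE summary is affected.* Section 10.1 also summarizes AEs, not only TEAEs, by maximum severity.
- *Recurrences of resolved events are wrongly dropped.* The text does not say whether a resolved event counts as present before dosing. Either treatment is a convention, and nothing in the SAP contradicts it.

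**Conclusion.** The concern holds in this limited form. As written, the onset clause takes all 28 follow-up days from a completer (16.6% of a 169-day window), 14 days from a subject with last dose on Day 127, and none from a subject with last dose on or before Day 113. The tables affected by lost follow-up onsets are the TEAE, SAE, related-event and AESI tables. Separately, a pre-dose event held as one continuing record cannot become treatment-emergent by worsening, against the evident purpose of the second alternative.

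These results rest on reading the treatment period as Section 3.2 defines it, on a completer's last dose falling on Day 141, and, for the worsening point, on the record being continued and not re-entered. The percentages are shares of time, not of events; the SAP gives no event rates. This should be corrected before the tables are programmed, but it does not touch the efficacy analysis.

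**What to change.** Replace the definition in Section 10.1 with one sentence:

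> *A TEAE is any AE with onset, or any increase in severity of an AE present before first dose, on or after the first dose of study medication and up to 28 days after the last dose.*

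Remove the condition that the event must start within the treatment period. The separate 28-day sentence then becomes redundant and can go. Classification by preferred term can stay for tabulation.

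The cost is a change of SAP wording and of the TEAE flag in the program. Onset dates and severity are already used in Sections 6 and 10.1, so no new collection is foreseen. For continuing records, confirm that the CRF shows when severity increased. The drawback is slightly higher TEAE counts.
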